### *12.3.2 Multi-center Studies*

Randomization will be stratified by center to preserve a balance across treatment groups. Center effects will be examined as permitted by sample size.

### *12.3.3 Multiple Comparisons and Multiplicity*

Since this is an exploratory Phase II study, analyses should be considered descriptive and no adjustments for multiple comparisons will be made.

### *12.3.4 Examination of Subgroups*

All analyses will be stratified by age group children under 18 and adults 18 and over.

### *12.3.5 Missing Data*

Data from patients who are lost to follow up will be used as much as possible since the analyses allow for missing data. If deemed necessary, a comparison of completers versus non-completers will be performed.

## 12.4 Statistical Methods

### *12.4.1 Study Population*

Patient disposition, populations, demographic and baseline information will be summarized by age strata and treatment arm.

### *12.4.2 Efficacy*

The goal of this study is to obtain laboratory and clinical information to justify a phase III clinical trial and to provide data to generate accurate power calculations for a subsequent phase III clinical trial. The two age groups (children and adults) will be analyzed separately to assess for differences in response to arginine therapy.

The laboratory variables NO, Gardos Channel activity, sickle red cell density (% of cells >41, as measured by Advia) are of primary interest. Additionally, sVCAM, H3 Technicon, Nitrotyrosine, 8-iso-PGF2 $\alpha$ , Ektacytometry, ET-1, and ECHO will be measured and analyzed as secondary efficacy variables. Since the goal of this protocol is to gain insight into the effect of arginine on multiple physiologic measures (e.g. erythrocyte characterization, endothelial function and free radical biology), we will model the change from baseline for all of the collected measurements over time using random effects longitudinal mixed models, with treatment and baseline measurement as fixed effects. This class of model allows us to control for the correlation induced by having multiple measurements on an individual. We will focus on estimating the relationship between each of the laboratory measures and treatment group over time.

Additionally, by judiciously choosing the structure of the fixed effects over time, we can investigate non-linear dose relationships as well.

Each laboratory measurement will be summarized by age group (pediatric and adult), treatment arm, and measurement time.

Clinical efficacy is a secondary endpoint for this trial. Clinical efficacy data will be collected on all patients. Specifically, patients will be asked for information on emergency room visits and hospitalizations, clinic visits for pain, and pain medication use. All clinical efficacy measurements will be summarized by age group, treatment arm, and measurement time (where applicable). Treatment differences may be examined using appropriate methods as the data permits.

All efficacy data will be analyzed descriptively to provide information for future trials. All analyses will be performed on the intent-to-treat population. Model assumptions will be confirmed and if broken, appropriate methods will be investigated.

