### 7.2 Description of Type of Study

The general research design of this proposal is a double blinded, placebo-controlled, Phase II trial of oral arginine in SCD patients. Due to concern over differences in response due to age, two age groups will be tested independently—children under 18 and adults 18 and over. Patients in each age group (children and adult) will be treated with one dose of arginine (0.05 g/kg/day) or placebo divided for BID dosing. Sixteen patients will be randomized to the arginine and placebo arms. Added to this will be the 16 children and 14 adults previously randomized to the high dose arginine arm (0.10 g/kg/day). In total, 94 patients (48 children and 46 adults) will be evaluated as to the effects of arginine.

**Figure 7.1.** Study Design

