## 12 STATISTICAL ANALYSIS

### 12.1 Sample Size

A total of 94 patients will be enrolled into this trial over an 18-month period (48 children and 46 adults). It is estimated that 6 to 8 clinical centers (12-16 patients per center) will be required to enroll sufficient patients in this period.

Initially, subjects were randomized to one of three treatment groups: placebo, low dose arginine and high dose arginine. With this amendment, subjects are now only randomized to placebo and low dose arginine. Subjects will be stratified by age group (5-17 years,  $\geq 18$  years) and since there could be drastic differences between these groups, they will be analyzed separately. Thus, all sample size calculations will be for each of these two groups.

We have identified three measurements that are of primary interest: Nitric Oxide, Gardos Channel Activity, and erythrocyte density (MCHC  $>41$ ). We will measure our panel of investigative laboratory measures at various time points between baseline and sixteen weeks (up to eight timepoints). In order to avoid making more assumptions than necessary for our sample size calculations, we will use a simpler model that reflects a single timepoint. Specifically, we will use a one-way ANOVA with three groups (one for each treatment arm) modelling the change from baseline in each of our three measurements. We will additionally assume a two-sided alpha of 0.05. The hypothesis tested from this model will be any difference in mean change from baseline between the three treatment groups.

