The literature suggests that the average NOx level in stable sickle cell patients is 25.5, with a standard deviation of 2.2. We assume that both groups start out with this mean and that the placebo group maintains this level across the length of the study. Based on preliminary findings, we expect a minimum increase of 1.75 for the high dose in the mean change from baseline NOx and the low dose to have a related 1.375 increase. If we assume that the variance is equivalent for the pre and post measurements, we can calculate the variance of the difference as the sum of the pre and post variances minus twice the covariance between pre and post measurements. Thus, our variance estimate depends greatly on the correlation between the pre and post measurements. Assuming a range of correlations (0.3, 0.5, and 0.7), we can then estimate the sample size we will need to detect the differences of 1.375 and 1.75 at 80% and 90% power. (See table below.)

Total sample sizes (for each age group) by power and correlation for NOx assuming a 1:1:1 randomization.

		Power	
		80%	90%
Correlation	0.7	27	33
	0.5	42	54

	0.3	57	72
--	-----	----	----

Given that the goal of this trial is exploratory, not confirmatory, we do not need to achieve a significant value on any specific hypothesis test. Additionally, a much larger treatment effect is anticipated, potentially giving us more power. Thus, a reasonable sample size to achieve our goals and provide us with a reasonable estimate, with the potential to see a significant effect is in the range of 48 total subjects in each age group. With the elimination of one dose of Arginine, the sample size of 16 adults per remaining treatment group will be used.

Insufficient data is available in the literature at this time to sufficiently estimate the expected within subject variability (at steady state of SCD) for the Gardos Channel Activity and erythrocyte density (MCHC >41) as measured by Advia. Sample size calculations would therefore be based on unfounded assumptions and are therefore not provided.

Since the rate of dropout cannot be estimated at this time, completion of the study will be monitored and dropouts will be replaced as they occur. This should pose no problem due to the relatively short duration of the trial. All available data on dropouts will be used in the analyses.

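### Separate analyses of children and adults, as written, give no estimate of the age difference in response that they are meant to assess

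*Protocol*

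**What the plan says.** Section 12.4.2 gives both a method and its purpose: "The two age groups (children and adults) will be analyzed separately to assess for differences in response to arginine therapy." The other sections that deal with age repeat the separation:

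- Section 7.2, citing concern that response may differ with age: "two age groups will be tested independently".
- Section 12.1: "since there could be drastic differences between these groups, they will be analyzed separately". The sample size is worked out within each age group.
- Section 12.3.4: "All analyses will be stratified by age group children under 18 and adults 18 and over".

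The model terms named in the synopsis (Data Analyses) and section 12.4.2 are treatment, baseline value, visit time and a random intercept per patient, fitted within each age group. No section names a comparison between the age groups or an age-by-treatment term.

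Sections 12.1, 12.3.3 and 12.4.2 also call the study exploratory and the analyses descriptive, and section 12.1 says that no particular test has to be significant.

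**The concern.** The stated aim and the stated method do not match. To say whether children and adults respond differently, one needs the effect in children minus the effect in adults, with its uncertainty. Two models fitted apart give the two effects and leave that last step undone.

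This goes beyond detail that a protocol may leave to an analysis plan, because section 12.4.2 itself names separate analysis as the way to assess the difference. It also bears on the stated goal of planning a phase III trial: whether children and adults can share one design, with one assumed effect, turns on this contrast. Without it, a reader may treat a significant result in one group and a non-significant result in the other as evidence of an age effect.

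**Working it through.** **Inputs (sections 7.2 and 12.1).** NOx in stable patients "is 25.5, with a standard deviation of 2.2"; pre-post correlation ρ of 0.3, 0.5 or 0.7; placebo change 0, low-dose effect 1.375, high-dose effect 1.75; 16 low dose and 16 placebo per age group; earlier high-dose arm of 16 children and 14 adults. On alpha: "We will additionally assume a two-sided alpha of 0.05." The sizing test is a three-group one-way ANOVA for "any difference in mean change from baseline between the three treatment groups".

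**Step 1: SD of the change.** SD = 2.2 × √(2(1 − ρ)), which is 2.603, 2.200 and 1.704 at ρ = 0.3, 0.5 and 0.7.

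**Step 2: the plan's own table.** Smallest equal-arm total N per age group for 80%/90% power, from the noncentral F distribution:

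| ρ | Printed in 12.1 | Effects 0, 1.375, 1.75 | Effects 0, 1.375, 2.75 |
|---|---|---|---|
| 0.7 | 27/33 | 54/69 | 27/33 |
| 0.5 | 42/54 | 87/114 | 42/54 |
| 0.3 | 57/72 | 120/156 | 57/72 |

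The printed effects do not reproduce the table; a high-dose effect of 2.75 does, in all six cells. Section 12.1 should reconcile this. It matters here because F-test results depend on which value is used, so both are carried forward.

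**Step 3: chance that exactly one age group has p < 0.05 when true effects are equal.** With power p_C in children and p_A in adults, this is p_C(1 − p_A) + p_A(1 − p_C). It cannot exceed 50% when the two powers are equal.

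*Low dose v placebo, 16 v 16.* This is the only comparison still being randomised. Noncentrality is 1.375 / (SD × √(2/16)) on 30 degrees of freedom.

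| ρ | Noncentrality | Power p | 2p(1 − p) |
|---|---|---|---|
| 0.3 | 1.494 | 30.4% | 42% |
| 0.5 | 1.768 | 40.2% | 48% |
| 0.7 | 2.282 | 59.8% | 48% |

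A simulation at ρ = 0.5 gave 48.2%.

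*Three-group F test, 16/16/16 children and 16/16/14 adults.*

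| ρ | High-dose effect 1.75: power C/A | Exactly one | High-dose effect 2.75: power C/A | Exactly one |
|---|---|---|---|---|
| 0.3 | 39%/38% | 47% | 74%/71% | 40% |
| 0.5 | 53%/51% | 50% | 87%/85% | 24% |
| 0.7 | 76%/74% | 38% | 98%/98% | 4% |

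*Sensitivity.* Adjusting for baseline, with residual SD 2.2 × √(1 − ρ²), gives 44% to 50% for low dose v placebo.

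**Step 4: what a direct contrast would give.** The contrast is (low dose − placebo in children) − (low dose − placebo in adults), with four cells of 16. SE = SD × √(4/16) = SD/2. The last two columns use the normal approximation.

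| ρ | SE | 95% CI half-width (1.96 × SE) | Difference detectable with 80% power (2.80 × SE) | Power if one group gains 1.375 and the other 0 |
|---|---|---|---|---|
| 0.3 | 1.30 | 2.55 | 3.65 | 18% |
| 0.5 | 1.10 | 2.16 | 3.08 | 24% |
| 0.7 | 0.85 | 1.67 | 2.39 | 36% |

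With equal effects, a test of this contrast is falsely positive 5% of the time. The detectable difference is 1.7 to 2.7 times the assumed low-dose effect (2.39/1.375 and 3.65/1.375), so at this size the contrast is useful as an estimate with its interval and is weak as a test.

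**The case against.** **The protocol does not propose to compare p-values.** This stands. A reader might infer from section 12.4.2 that an age difference will be declared when one group is significant and the other is not, and so that a false age difference is likely to be reported. The documents do not support that. The efficacy analyses are called descriptive, the stated focus is estimation, and alpha appears only in the sample size section, as a planning assumption, and not as a decision rule for efficacy. The percentages in Step 3 measure a possible misreading.

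**The figure near one half is conditional.** This also stands. It holds for low dose v placebo. For the F test on which the trial was sized, the range is 4% to 50%.

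**Separate analyses do not rule the comparison out.** True: the groups contain different patients, so the two estimates and standard errors could be subtracted. To say that the trial cannot address the question would go too far. But the protocol does not name that step, and it presents separation itself as the assessment.

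**Not pooling is a reasoned choice.** A reader might go on to argue that the trial should pool the age groups for power. Sections 7.2 and 12.1 give a reason against pooling, namely that response may differ markedly with age, and any gain from pooling assumes similar effects. The same reason makes an estimate of the difference more useful.

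**The contrast will be imprecise.** True, as Step 4 shows. That limits what can be concluded about age; it does not justify leaving the uncertainty unstated.

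**Conclusion.** The point holds as a mismatch between aim and method. Section 12.4.2 says that separate analyses will assess age differences in response, yet no analysis in the protocol yields that difference or its interval.

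For size: with equal true low-dose effects, a reader comparing significance would see exactly one significant age group in 42% to 48% of trials. This assumes NOx at a single timepoint, SD 2.2, an effect of 1.375, 16 v 16, and correlations of 0.3 to 0.7. It cannot be extended to Gardos channel activity or red cell density, for which section 12.1 gives no variability.

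The exploratory label softens the consequence but does not supply the missing estimate. This should be changed, at low cost; it does not undermine the trial.

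**What to change.** Keep every planned analysis and table by age group. In section 12.4.2 add, for each primary endpoint, one joint model with treatment, age group and treatment-by-age-group alongside the baseline, visit and patient terms already planned. State that the interaction estimate, with its 95% confidence interval, is the assessment of age differences, reported descriptively and without a significance rule. An age-stratified overall treatment effect is optional.

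If the joint model is not wanted, section 12.4.2 should say that each age group is described on its own and drop the claim that separate analysis assesses differences.

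The cost is three additional models, with no new data or patients. The drawback is imprecision: for NOx the interval will extend about 1.7 to 2.6 either side of the estimate, which is wider than the assumed effect of 1.375, and the report should say so plainly.

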#### *12.4.3 Safety Data*

The assessment of safety data will be based mainly on the tabulation of adverse events (AE), by age group and treatment arm. Additionally, AEs will be tabulated by severity and relationship to drug. Serious AEs will be described in detail. Additionally, blood chemistry, hematology, and urinalysis laboratory measurements will be tabulated by age group, treatment group, and measurement time. Other specific laboratory measurements, such as Met Hb, will also be collected and tabulated by age group, treatment group, and measurement time.

#### *12.4.4 Other Data*

In addition to the efficacy and safety laboratory measurements, blood levels of arginine and arginase will be measured. These measurements will be summarized by age group, treatment arm, and measurement time. Additionally, graphic displays may be produced to examine trends in absorption over time. A dose response analysis may be performed if the data warrants. Echocardiograms will also be collected baseline and at the end of treatment with arginine to determine if pulmonary artery pressure is reduced by therapy with arginine.

#### *12.4.5 Unmasked Interim Analysis and Masked Interim Data Monitoring*

No interim analyses will be performed in this study.

## 13 HUMAN SUBJECTS PROTECTION

### 13.1 Discontinuation of Study

The National Heart Lung and Blood Institute (NHLBI) reserves the right to discontinue the study at any time for administrative reasons. A data safety and monitoring board will monitor the trial by periodically examining the unblinded safety data. The DSMB can recommend discontinuation of the study due to safety concerns at any time. Investigators will be reimbursed for reasonable expenses incurred to the date of discontinuation on the basis of completed subjects.

There are few known risks associated with taking arginine and the safety of the subjects will be monitored by an independent data and safety review board. Subjects can withdraw from the study at any time. Discontinuation of any part of the protocol does not interfere with the patient receiving their routine medical care.

The benefits of improving our understanding the mechanisms and impact of taking arginine in patients with SCD strongly outweighs the minimal risks associated with this therapy. If efficacious, this therapy could be used at little cost to improve the disease progression in other SCD patients.

All data collected for the purposes of this study will be kept as confidential as other medical records. Data will be stored in one location in a locked filing cabinet to be accessed only by study personnel with the direct permission of the principal investigator. No names will appear on the data; however, subject materials will be identifiable through a unique code number assigned to the subject at the beginning of the study. This master list with the subject's name and his/her identification number will be locked in a separate filing cabinet to further ensure confidentiality. Any published findings as a result of the study will not identify participants by name.

### 13.4 Publication of Research Findings

Manuscript(s) and abstract(s) prepared from the data collected during this trial will be prepared by the study investigators and the SDMC.

**14 SUBJECT COMPENSATION**

Patients will receive \$500 for full participation in the study. Partial compensation will be given on a pro-rated basis based on number of study visits completed.

